4.5.2.3.1 Sensitivity Analysis

The following sensitivity analyses may be conducted if appropriate based on evaluation of data:

1. To examine the effect of subjects who discontinue for any reason prior to achieving a clinical response event
 - patients who are lost to follow-up or who do not have a clinical response event will be censored at 35 days.
2. To examine the effect of antipyretics on achieving clinical response
 - the restriction of antipyretics use within 8 hours on temperature condition will be removed
3. To examine the effect of inotropic support on achieving clinical response.
 - the restriction of no inotropic support within 2 hours.

4.5.3 Other Secondary Efficacy Endpoints

The other secondary efficacy endpoints for this study are as follows:

Incidence of mechanical ventilation

Incidence of mechanical ventilation, as defined as being on non-invasive mechanical ventilation, mechanical invasive ventilation or ECMO, will be assessed from the vital signs assessment log where the patients need for mechanical ventilation is documented. It will be assumed, unless the mechanical ventilation status has changed, that the first occurrence is continuous and as such will be counted as one event. This will also be the case for each subsequent event. If there is a missing status, and the prior and subsequent status are the same, it can be assumed this is the one continuous incidence of mechanical ventilation.

The number of incidences of mechanical ventilations between start of treatment and end of study, as well as number and percentage of patients, will be presented.

As an additional analysis, patients whose mechanical ventilation had started before being randomized into the study, who continued to be on mechanical ventilation after receiving first treatment will also be included in the number of incidences of mechanical ventilations. The number and percentage of patients will also be presented.

Duration of mechanical ventilation

Duration of mechanical ventilation, in hours, will be assessed from the vital signs assessment log where the patients need for mechanical ventilation is documented. The duration of mechanical ventilation will be defined as sum of the duration of each mechanical ventilation incidence. The duration of each incidence is defined as the date and time of the first occurrence of mechanical ventilation until the next date and time where the patient mechanical ventilation status has changed on the vital signs log. It will be assumed that, unless the mechanical ventilation status has changed, the first occurrence is continuous and as such will be counted as one event. This will also be the case for each subsequent event. Duration is calculated for events between start of treatment and end of study.

Patients who are on mechanical ventilation at the last vital signs assessment will use the imputation rules defined in [Table 8](#) below for calculation of the duration of last mechanical ventilation incidence. Missing and partial vital dates will be imputed based on available data, following a conservative approach.

Table 8 Duration of Mechanical Ventilation and Missing Data

Event	Imputation Rule
Patient Discontinued or Lost to follow-up	duration of last incidence uses date of discontinuation or date lost to follow up as the end date
Patient died	duration of last incidence uses date of death as the end date

The analysis of duration of mechanical ventilation will be repeated to include patients whose mechanical ventilation had started before being randomized into the study, who continued to be on mechanical ventilation after receiving first treatment. The duration will be calculated as specified above, except it will start from the start date of mechanical ventilation.

Incidence of ICU stay

Incidence of ICU will be assessed from the ICU admissions log. It will be assumed that, unless a discharge date is available, the first ICU admission is continuous and as such will be counted as one event. This will also be the case for each subsequent event. The number of incidences of ICU stay as well as number and percentage of patients with ICU stay, between start of treatment and end of study will be presented.

This analysis will be repeated to include patients who were admitted to ICU prior to randomization in the study, but remained in ICU after first treatment. The number of incidences of ICU stay, and the number and percentage of patients with ICU stay whilst on treatment will be presented.

Duration of ICU stays

Duration of ICU stay will be calculated in hours as the sum of the duration of ICU stay, based on the admission and discharge date and time of the ICU admissions log: (ICU discharge datetime – ICU admission datetime).

Patients who are in ICU until end of study will be censored at last available date and time. Patients who die will be censored at their date of death.

Partial admission and discharge dates and times will be imputed based on available data, following a conservative approach.

This analysis will be repeated to also include patients who were admitted to ICU prior to randomization in the study, but remained in ICU after first treatment.

Time to clinical failure

Time to clinical failure, in hours, is defined as the time from start of treatment to death, mechanical ventilation, or ICU admission, corresponding to ordinal scale categories 6, 5, and 4, respectively.

For patients who are on mechanical ventilation, or in ICU without mechanical (invasive) ventilation at start of treatment the time to clinical failure is calculated as time to worsening condition i.e. for patients with ordinal scale of 4 (ICU admission without mechanical [invasive] ventilation) at start of treatment worsening is defined as a mechanical ventilation or death), for patients with ordinal scale 5 (mechanical ventilation) at start of treatment worsening defined as a death.

Intercurrent events, such as patients who are lost to follow-up, or discontinue for any reason prior to clinical failure or do not have clinical failure, will be accounted for through censoring rules, as described in [Table 9](#) below.

Table 9 Time to Clinical Failure and Censoring

Event	Censor	Date and Time
Clinical Failure (death, mechanical ventilation, or ICU admission)	No	first occurrence of death, mechanical ventilation, or ICU admission post baseline
Death	No	date of death
Discontinuation but subsequently reported death	No	date of death
Discontinuation for any reason prior to having clinical failure	Yes	censored at last vital signs assessment
Lost to follow-up	Yes	last available date
No clinical failure	Yes	last available date

Time to hospital discharge

Time to hospital discharge, in hours, is defined as the time from start of treatment to time of discharge from hospital. Patients who are lost to follow-up, die or discontinue for any reason prior to discharge or who are not discharged will be censored at the time of their last assessment or date of death, whichever is applicable, as per rules presented in [Table 10](#) below.

Table 10 Time to hospital discharge and Censoring

Event	Censor	Date and Time
Hospital discharge	No	hospital discharge
- hospital discharge to another hospital (i.e. hospital admission within 24 hours) and discontinue study on same day	Yes	hospital discharge
- hospital discharge to another hospital (i.e. hospital admission within 24 hours) and continue study	Yes	hospital discharge
- hospital discharge against medical advice (i.e. self-discharge)	Yes	hospital discharge
- all other hospital discharge	No	hospital discharge
Death prior to hospital discharge	Yes	last vital signs assessment prior to death
Discontinuation for any reason prior to hospital discharge	Yes	last vital signs assessment prior to discontinuation
Lost to follow-up	Yes	last vital signs assessment
No hospital discharge	Yes	last vital signs assessment

Incidence of influenza-related complications

Influenza-related complications are recorded on specific complication eCRF pages with diagnostic questions for the complications of pneumonia, myositis or rhabdomyolysis, encephalitis or encephalopathy, myocarditis and/or pericarditis, otitis media, sinusitis, exacerbation of COPD/asthma, sepsis, acute lung injury or acute respiratory distress syndrome. These eCRF pages will be utilized for these specific events when they are reported as adverse events after the initiation of study treatment. This data will be subject to an internal blinded manual medical review of events together with other related eCRF data (e.g. serious adverse event forms as applicable and medical history). The objective of the review is to ensure that sufficient clinical evidence for each individual reported complication event has been provided through the recorded CRF data to support the diagnosis.

The number and percentage of patients, as well as the number of events, will be presented by treatment group as follows:

- all events,
- internally adjudicated events,
- investigator assessed related to influenza events and
- investigator assessed related to influenza and internally adjudicated events will be presented.

The process by which internal adjudication of influenza related complications will be conducted is outlined in a separate charter.

Mortality rate at Day 7

The mortality rate is defined as the number of patients who died on or before Day 7.

If date of death is not recorded for any patient who has died, the last known date where the patient was alive will be used to ascertain if they were alive at Day 7.

Mortality rate at Day 28

The mortality rate is defined as the number of patients who died on or before Day 28.

If date of death is not recorded for any patient who has died, the last known date where the patient was alive will be used to ascertain if they were alive at Day 28.

Time to NEWS2 of ≤ 2 maintained for 24 hours

Time to NEWS2 of ≤ 2 maintained for 24 hours is defined as the time from start of treatment to the point at which NEWS2 assessment score ≤ 2 is reached and must be maintained for 24 hours. Patients who are lost to follow-up, die or discontinue for any reason prior to achieving NEWS2 of ≤ 2 for 24 hours will be censored at the time of their last assessment or date of death, whichever is applicable, as per rules presented in [Table 11](#) below.

Table 11 Time to NEWS2 of ≤ 2 maintained for 24 hours and Censoring

Event	Censor	Date and Time
NEWS2 ≤ 2 for 24 hours	No	vital signs assessment where NEWS2 ≤ 2 at start of 24 hour period
NEWS2 ≤ 2 prior to discharge	No	first vital signs assessment where NEWS2 ≤ 2 prior to discharge
Death prior to achieving NEWS2 ≤ 2 for 24 hours	Yes	last vital signs assessment prior to death
Discontinuation for any reason prior to achieving NEWS2 ≤ 2 for 24 hours	Yes	last vital signs assessment prior to discontinuation
Lost to follow-up	Yes	last vital signs assessment
No NEWS2 ≤ 2 for 24 hours	Yes	last vital signs assessment

Incidence and rate endpoints will be analyzed using the Cochran Mantel-Haenszel test statistic stratified by region (North America, EMEA, ROW), NEWS2 at baseline (≤ 7 , >7) and time from symptom onset to study treatment (≤ 48 hours, > 48 hours).

Time to event secondary efficacy endpoints will be analyzed using the same method and sensitivity analyses (where required) as specified for the primary endpoint (see Section 4.5.1).

Mortality rates and duration of ICU stays and ventilation will be analyzed descriptively.

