4.5.4 Vital Signs

Vital signs will include measurements of respiratory rate, pulse rate, peripheral oxygen saturation, systolic and diastolic blood pressures, and body temperature. Body temperature should be measured using the same methodology throughout the study.

For patients requiring supplemental oxygen, the oxygen flow rate (L/min) and/or fraction of inspired oxygen (FiO_2) should be recorded.

All of the vital sign parameters should be recorded *together* four times per day for the duration of the hospitalization throughout the treatment period (Day 1/Visit 1 to Day 10). It is recommended that the collection timepoints for vital signs and assessments (specific to NEWS2, Section 4.5.4) are spread throughout the study day to reflect the patient's condition over the entire study day, where possible. Following hospital discharge during the treatment period (Day 1 to Day 10) these parameters should be recorded once at each return visit to the clinic. Patients who remain hospitalized during the follow-up period (Day 11+) require daily collection of vital signs for the purpose of the study. During the follow-up period in patients who have been discharged, vital sign measurements and temperature are to be recorded at the investigators' discretion (e.g., if symptoms and signs persist during follow-up). Vital sign measurements may be performed by an MN professional.

4.5.5 Assessments Specific to National Early Warning Score 2

In addition to the vital measurements, the patient's consciousness level and the presence or absence of respiratory support must be recorded. The NEWS2 parameter for respiratory support is the selection of either air or oxygen –“oxygen” can include other forms of ventilation to maintain oxygen saturation (see [Appendix 3](#)).

These should be recorded at the same time points as the vital sign measurements (see Section 4.5.4 and [Appendix 1](#)).

4.5.6 National Early Warning Score 2

The NEWS2 should be calculated by the site at screening only based upon vital sign values and assessments related to National Early Warning Score 2 (see Section 4.5.5) recorded during the patient assessment. Should these assessments be conducted more than once during the screening period (per site patient care), all data collected closest to but before randomization should be used for the NEWS2 score calculation and assessment of patient eligibility. See [Appendix 3](#) for calculation instructions.

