5.3.5.10 Hospitalization or Prolonged Hospitalization

Any adverse event that results in hospitalization following initial discharge (i.e., in-patient admission to a hospital) or prolonged hospitalization (i.e., after the current study hospitalization) should be documented and reported as a serious adverse event (per the definition of serious adverse event in Section 5.2.2), except as outlined below.

An event that leads to the prolongation of hospitalization under the following circumstances should not be reported as an adverse event or a serious adverse event:

- Hospitalization for respite care
- Hospitalization for a preexisting condition, provided that all of the following criteria are met:
 - The hospitalization was planned prior to the study or was scheduled during the study when elective surgery became necessary because of the expected normal progression of the disease.

The patient has not experienced an adverse event.

An event that leads to the prolongation of hospitalization under the following circumstances is not considered to be a serious adverse event, but should be reported as an adverse event instead:

- Hospitalization that was necessary because of patient requirement for outpatient care outside of normal outpatient clinic operating hours
- Adverse events that would otherwise not require hospitalization

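### Incidence and duration of mechanical ventilation are reported to end of study from a log that requires no readings in discharged patients from Day 11, so ventilation on readmission can go uncounted

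*SAP*

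**What the plan says.** SAP 4.5.3 defines ventilation broadly: invasive, non-invasive or ECMO. Incidence and duration have the same single source; each "will be assessed from the vital signs assessment log where the patients need for mechanical ventilation is documented". Both run over the whole study. For incidence, what is presented is "The number of incidences of mechanical ventilations between start of treatment and end of study", with the number and percentage of patients. For duration, "Duration is calculated for events between start of treatment and end of study". An episode lasts from its first logged occurrence "until the next date and time where the patient mechanical ventilation status has changed on the vital signs log".

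Protocol 4.5.4 and the notes to the Schedule of Activities (Appendix 1) set how often that log is filled:

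- Inpatients to Day 10: "four times per day for the duration of the hospitalization throughout the treatment period (Day 1/Visit 1 to Day 10".
- Inpatients afterwards: "Patients who remain hospitalized during the follow-up period (Day 11+) require daily collection of vital signs for the purpose of the study". The schedule confines Day 11+ hospital procedures to patients who have stayed in hospital.
- Discharged patients to Day 10: one reading at each return visit. Visits 1 to 7 apply to everyone, discharged or not.
- Discharged patients from Day 11: "in patients who have been discharged, vital sign measurements and temperature are to be recorded at the" investigators' discretion.

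The ICU endpoints in the same SAP section use a different source, an admissions log with admission and discharge dates and times.

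**The concern.** The stated window and the data behind it do not match. The endpoints claim coverage to end of study, but the only named source becomes sparse after Day 10 and, for anyone discharged, has no required entries from Day 11. A patient who is readmitted and ventilated in that period could be counted as never ventilated under the SAP as written.

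Such a patient would usually appear elsewhere in the database. Protocol 5.3.5.10 says that "Any adverse event that results in hospitalization following initial discharge" is to be reported as a serious adverse event, apart from listed exceptions. The SAP does not bring that record into these two endpoints.

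Coverage also depends on discharge, which is a component of the primary endpoint. The arm that discharges earlier has fewer required readings, so missed events would tend to flatter it. Ventilation is an outcome readers will look at closely, and SAP 4.5.3 gives incidence endpoints a stratified Cochran-Mantel-Haenszel test.

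**Working it through.** The documents give no rate, event count or power for ventilation, so there is no planned figure to reproduce. The check counts required readings and asks what they can detect.

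**Inputs**
- Reading frequencies: Protocol 4.5.4 and the Appendix 1 notes, as set out above.
- Visit days after Day 1: 2, 3, 4, 5, 7 and 10 (Appendix 1).
- Study length: 35 days, made up of 10 treatment and 25 follow-up (Protocol 3.1).
- Assumption: readings are evenly spaced, so the gap is 6 h at four a day and 24 h at one a day. The protocol only recommends spreading them through the day.

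**Step 1. Required readings by last inpatient day d**

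Readings = 4 × min(d, 10) + max(0, d − 10) + number of visit days later than d.

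| Last inpatient day | In hospital | Return visits to Day 10 | Total | Days with none required |
|---|---|---|---|---|
| 3 | 12 | 4 | 16 | 28 |
| 5 | 20 | 2 | 22 | 28 |
| 7 | 28 | 1 | 29 | 27 |
| 10 | 40 | 0 | 40 | 25 |
| 14 | 40 + 4 = 44 | 0 | 44 | 21 |
| 35 | 40 + 25 = 65 | 0 | 65 | 0 |

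For anyone discharged by Day 10, no reading is required on Days 11 to 35: 25/35 = 71% of the window.

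**Step 2. Chance that an inpatient episode of length L meets at least one reading**

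P = min(1, L/gap).

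| Episode | To Day 10 (gap 6 h) | After Day 10 (gap 24 h) |
|---|---|---|
| 3 h | 50% | 12.5% |
| 6 h | 100% | 25% |
| 12 h | 100% | 50% |
| 18 h | 100% | 75% |
| 24 h or more | 100% | 100% |

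Only episodes shorter than 24 h are at risk in patients still in hospital after Day 10. These are plausible because non-invasive ventilation counts.

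**Step 3. Duration**

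On an even grid, late-recorded starts and late-recorded ends cancel, so mean duration over all episodes is not biased. A 12 h episode on daily readings is recorded as 24 h half the time and 0 h half the time: 0.5 × 24 + 0.5 × 0 = 12 h. Individual values become all-or-nothing.

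**Step 4. Other records**

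- Ordinal scale category 5 (Protocol 4.5.16): invasive ventilation only, once each morning while in hospital.
- Adverse events (Protocol 5.3.1): to 28 days after the last dose, which is Day 4 + 28 = Day 32 after two doses and Day 7 + 28 = Day 35 after three.
- ICU admissions log: to end of study, but category 4 of the ordinal scale is ICU without invasive ventilation, so admission does not establish ventilation.

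**The case against.** The strongest reply is that little is lost. Discharged patients are at low risk. Those still in hospital have any episode of 24 h or more logged. Both endpoints are outside the testing hierarchy (SAP 4.5), and duration is descriptive. Late deterioration also shows in ICU stay, time to clinical failure, complications and SAEs. All of this stands, and it keeps the point modest. It does not supply a source for post-discharge ventilation in these two endpoints.

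The position of transferred patients is open. Protocol 4.5.4 does not limit inpatient readings to the first hospital, so it cannot be said that a transferred patient has no required entries. SAP Tables 7 and 10 recognise transfer with continued participation, but the log requirement is not spelled out.

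A reader might infer more than the documents support:

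- **That nothing is required after discharge.** One reading per return visit is required to Day 10. It would seldom show ventilation, since the patient is attending a visit, but it is required.
- **That a 31-hour benefit means 31 hours less observation.** The 31 h in SAP 2.4 is a difference in TTCI, which NEWS2 can meet before discharge. It is not a shorter stay.
- **That a large share of ventilated patients is lost.** Assuming in-hospital ventilation in 5% to 10% and post-discharge ventilation in 0.5% to 2%, the missed share runs from 0.5/10.5 = 4.8% to 2/7 = 28.6%. Those rates are assumed, the calculation treats every post-discharge event as unlogged, and the loss would fall on both arms about equally.
- **That the comparison is materially biased.** As an illustration, suppose stay really were 31/24 = 1.29 days shorter. Protocol 1.1 gives stays of 5 to 9 days, leaving 30 to 26 days after discharge. With the same assumed 0.5% to 2% spread evenly, the extra unobserved risk is between 1.29/30 × 0.5% = 0.02% and 1.29/26 × 2% = 0.10%, or about 0.04 to 0.17 of the 176 planned baloxavir patients. It would be larger if risk clustered just after discharge, but could not exceed the assumed rate itself.

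**Conclusion.** The point holds as a mismatch between window and source. SAP 4.5.3 promises ventilation to end of study from a log with no required entries in discharged patients for 25 of 35 days, thinner inpatient readings after Day 10 and no express requirement on readmission. Two kinds of event can be missed: ventilation after discharge or on readmission, and inpatient episodes under 24 h after Day 10. The detection figures for short episodes assume evenly spaced readings.

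Any bias between arms would favour the one that discharges earlier. Its size cannot be derived from the documents, which give no readmission or post-discharge ventilation rates, and it is probably small. The case for change is that the endpoint should mean what its label says and use evidence the trial already collects; a distorted treatment comparison has not been shown.

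**What to change.** In SAP 4.5.3:

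- Count a patient as ventilated if the vital signs log, ordinal scale category 5 (invasive only), or an AE/SAE record documents ventilation, including records from readmissions and transfers.
- Use ICU admissions log entries only to prompt a check for ventilation, never as an event in themselves.
- Make number and percentage of patients the main incidence summary. Episode counts depend on reading frequency, and merging neighbouring episodes would not cure that, because an episode lying between two readings is never logged.
- If reconciliation is not done, restate both endpoints as covering the index hospitalization and remove the reference to end of study. Keep inpatient days after Day 10; cutting at Day 10 would discard valid data.

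The cost is SAP wording, derivation programming and a review of AE/SAE records before unblinding. Some episodes taken from AE/SAE pages will have dates without times, so their durations will be coarser. Non-invasive ventilation after discharge will be recovered only where an AE/SAE record mentions it, and routine AE reporting ends around Day 32 for patients given two doses.
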